Snapchat is a mobile app for Android and iOS devices that is primarily a photo based social media platform. It has over 80 million users in the United States. In terms of age distribution, 69% of teenagers, and 24% of adults use the platform. Among teenagers, it is the social media platform that they use most often.^{9,10} While most “snaps” are made available to the receiver for only a short time before it becomes inaccessible, Snapchat has a “snapcode” feature that functions similarly to QR reader. This can be used to open an internet link through the Snapchat application. A previous study has used this feature to promote reproductive health education in hospitalized adolescents.¹⁷

Social media is now a part of daily life for the majority of Americans and particularly for adolescents. Given that social media is already a forum utilized by our patients and families, using it seems like a promising resource inexpensive modality to provide consistent asthma education.

Specific Aims:

[figure not shown]
1. To randomize 200 eligible children with asthma to social media enhanced education or to usual care to evaluate whether SME will:
 - a. Reduce total number of treatment days defined as summation of days of subsequent hospital admission, emergency room visits, and clinic visits
 - b. Reduce missed school days
 - c. Reduce total costs from a health system perspective
 - d. Have increased effect with increased social media engagement
 - e. Have increased effect in participants with both caregiver and patient (combined) with social media accounts, compared to participants where only the patient or only the caregiver uses social media (single)
 - f. Have increased patient satisfaction in the asthma education received
2. To obtain the experience and data needed to refine SME to be able to expand this platform for other chronic medical conditions with high healthcare utilization including pediatric diabetes, epilepsy, and sickle cell disease

Hypotheses: Social media enhanced education will result in

1. Reduction in treatment days in a medical setting from enrollment to one year from enrollment (primary hypothesis)
2. Reduction in missed school days
3. Reduction in total health system costs
4. Increased treatment effect in those patients with high social media engagement compared to low social media engagement
5. Increased treatment effect in those with combined (patient + caregiver) social media accounts compared to single participants

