6. Increase in patient satisfaction of amount and frequency of asthma education.

Study Design and Methods:

Logic Model: Using Social Media to Enhance Asthma Education

Population: We will recruit children age 3-17 years old hospitalized to Children's Memorial Hermann admitted for asthma exacerbation. To be eligible, the patient and/or primary caregiver must have internet access on cellular phones or at home and use a social media account (Facebook, Twitter, Instagram, and/or Snapchat). Exclusion criteria include children with other chronic conditions besides asthma that may necessitate frequent health care utilization. i.e. children with complex chronic conditions, sickle cell, seizures, diabetes. Children less than 3 years are excluded as a formal diagnosis of asthma prior to this age is difficult, and we aim to homogenize the population and exclude similar diagnoses such as bronchiolitis or wheezing of infancy.

Randomization, Consent, Allocation, Blinding: The PI (RPC) will be primarily responsible for enrollment and randomization. We will submit our study to the UTHealth Institutional Review Board as a quality improvement (QI) trial to verify the benefits of an intervention to increase access to asthma education beyond what would otherwise be provided in usual care. As allowed under federal regulations for QI studies judged unlikely to increase patient risk,²³⁻²⁵ we will request waiver of consent from the IRB, but we plan to still seek verbal permission to be able to contact patients monthly to assess their healthcare utilization.

Block randomization with variable block sizes and stratification by age will occur. Stratification for age will occur, (3-11 years or 12-17 years) to allow for equal allocation of teenagers to each arm. Allocation ratio of 1:1 will be used. Patients will be randomized during their hospitalization. While patients and caregivers cannot be blinded, the statistician and healthcare economist will be.

Interventions:

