3. Participants will have an informal avenue of communication to the team by tweeting questions or comments to the team.

Instagram

The research team will post photos and short videos to be shared with participants. Participants can comment on the posts to discuss or ask questions to the team.

Snapchat

The research team will post pictures and videos similar to the Instagram platform. The team will also create snapcodes that link participants to our cloud based asthma education website run via google drive. This will allow for text based education along with the typical photo based content of this platform.

Outcomes:

Primary Outcome: Total number of treatment days in a medical setting (hospital, ED, clinic) within one year of enrollment. Treatment days are defined as the summation of days in the hospital, ED, or in the clinic. We chose one year because of the chronicity of asthma, as well as its seasonal variation.

Secondary Outcomes: Total number of hospitalizations, total number of readmissions, total number of emergency room visits, and the total number of clinic visits, patient satisfaction and understanding of asthma education, number of missed days of school, and total estimated health system costs, hospital costs, and clinic costs.

Healthcare utilization will be primarily assessed by parental report. The PI will contact families every month and ask if their child had been admitted, visited the emergency room, had a clinic appointment for asthma, or missed any days of school within that month. We will also verify utilization of any of the 14 Memorial Hermann hospitals (MHHS) and the UT Health clinics from their respective electronic medical records and claims data. While we are aware of the risk of recall bias, we believe a contact every month is frequent enough to minimize the bias. We will also obtain multiple ways of contact (phone call, text, email, social media) in order to reduce loss to follow up.

Level of engagement will be tabulated by the following: Facebook engagement will be tracked through “likes,” comments, unfriending, completion of learning units, completion of polls. Twitter engagement will be tracked through “retweets,” comments, completion of polls, and unfollowings. Instagram engagement will be tracked by “likes,” comments, and unfollowings. Snapchat engagement will be tracked by number of snapcode links viewed, and any unfollowings.

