Hospital and clinic costs will be assessed from the health system perspective. For each ED visit and hospitalization in the MHHS, total hospital-specific costs will be obtained from the cost-accounting system for these hospitals. Costs for physician services provided at CMHH will be estimated using UTHealth claims data and Relative Value Units (RVUs) from the Medicare Fee Schedule. The costs at other hospitals outside MHHS will be estimated based on the mean costs of these encounters at MHHS. Costs for clinic visits at UT Health will be estimated using UTHealth claims data and using the standard RVU-based method. The costs for office visits occurring outside our center will be estimated based on the mean costs observed at UTHealth. For the social media intervention group, we will also add the costs of the personnel time spent curating and managing the educational material to be used in the social media platforms. The total time spent with the social media intervention will be prospectively collected by the PI (who will be primarily responsible for managing the social media intervention and will also include time from the pulmonologist [RM] and hospitalist [KS] whenever their input is required) and will then be multiplied by the unit time costs based on the personnel salary, fringes, and overhead costs. All costs will be inflated to the year of analysis based on the Consumer Price Index for medical services.

Data Analysis Plan:

Effect size, recruitment, power & statistical analysis

Based on retrospective data of patients hospitalized at CMHH as well as estimated national data,^{27,28} we estimate a 25% hospital readmission rate and 35% emergency visit rate within one year of discharge for those receiving usual asthma education. We also assume a 35% unplanned clinic visit rate within one year of discharge. Each admission accounts for 2.4 treatment days, and each clinic and ER visit accounts for 1 treatment day. In a population of 100 patients, we then expect the total number of treatment days to be 114 days or 1.14 days per child-year. With an expected 25% effect size (based on the 20%-30% effect size reported in the Cochrane reviews on the impact of asthma education on healthcare utilization among pediatric patients,⁴ recruitment of 200 patients will give 0.80 power to show reduction in total number of unplanned treatment days with probability of benefit >60%.

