Information to be gathered will be missed school days, total number of hospitalizations, emergency room visits, and clinic visits. We will also gather costs of these visits. Engagement data will be obtained from the various social media platforms.

Interpretation and Potential Importance of Findings:

If we are able to demonstrate successful effects of social media enhanced asthma education in decreasing unplanned healthcare utilization, we believe the impact to be substantial. First, there is a large disease burden. Asthma is the most common chronic disease in childhood that affects 5.5 million children in the United States. Second, the intervention is easily implementable since social media use is so ubiquitous. Third, the outcome of a cost dominant intervention has implications for tremendous savings on costs to the healthcare system. Compounding this, we think the results of the study would be easily generalizable – 1. To the adult population, encompassing another 19.2 million patients with asthma in the US (339 million worldwide), and 2. To other chronic pediatric medical conditions that have frequent unplanned healthcare utilization such as pediatric diabetes, sickle cell, and epilepsy.

Plans for Dissemination of Results:

Once the project is completed, we plan on dissemination of results through submissions to national conferences (Pediatric Academic Societies, American Academy Pediatrics, and Pediatric Hospital Medicine) as well as manuscript publication in a peer-reviewed journal (JAMA Pediatrics, Pediatrics, Hospital Pediatrics).

References

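### Hospital and ED days, and their costs, are not limited to asthma, while the clinic item of the monthly question is, so the primary total has no single stated cause

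*Combined protocol and SAP*

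**What the plan says.** The places that define or collect utilization do not agree on cause.

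- **Primary outcome (Outcomes):** "Treatment days are defined as the summation of days in the hospital, ED, or in the clinic". No asthma limit.
- **Aim 1a (Specific Aims):** "summation of days of subsequent hospital admission, emergency room visits, and clinic visits". No asthma limit.
- **Monthly contact (Outcomes):** the PI will "ask if their child had been admitted, visited the emergency room, had a clinic appointment for asthma, or missed any days of school". The words about asthma follow the clinic item.
- **Record check (Outcomes):** "We will also verify utilization of any of the 14 Memorial Hermann hospitals (MHHS) and the UT Health clinics". No diagnosis filter is given.
- **Costs (Outcomes):** "For each ED visit and hospitalization in the MHHS, total hospital-specific costs will be obtained". No diagnosis filter is given.
- **Data list (Study Procedures):** "total number of hospitalizations, emergency room visits, and clinic visits". No asthma limit.

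The Population paragraph removes some unrelated use: "Exclusion criteria include children with other chronic conditions besides asthma that may necessitate frequent health care utilization". Injuries, surgery and unrelated acute illness in otherwise eligible children remain. No section gives a rule for attributing an encounter to asthma.

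**The concern.** The 25% planning effect comes from reviews of asthma education, which has no evident way to change days spent in care for a fracture or appendicitis. Such days add about equally to both arms and move the rate ratio toward 1. The Data Analysis Plan rests the conclusions on the probability of benefit given the observed effect size, and that is the quantity that shrinks.

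Two further problems follow from the silence.

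- A clinic visit may be screened by the parent's stated reason, while the record check and the clinic costing carry no such screen. Care inside and outside the health system could then be counted by different rules.
- The PI enrols and randomizes, runs the posts and makes the monthly contacts. Only the statistician and the economist are blinded. Without a written rule, whether an encounter counts could be decided case by case by someone who knows the arm.

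**Working it through.** **Inputs from the Data Analysis Plan.** Usual-care rates are 0.25 readmissions, 0.35 ED visits and 0.35 clinic visits per child-year. An admission counts 2.4 days and each visit 1 day. The effect is 25%, the SD is 1.5 times the mean, and success is a posterior probability of benefit above 60%. The prior is centred at a relative risk of 1 with interval 0.3 to 3.0. With 1:1 allocation there are 100 children per arm.

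**Base mean.** 0.25 × 2.4 + 0.35 + 0.35 = 1.30 days per child-year. The plan states 1.14. I use 1.30 and show 1.14 as a check; the mismatch is a separate matter.

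**Assumption.** Let b be unrelated days per child-year, equal in both arms. The documents give no value, so b = 0.25, 0.5 and 1.0 are illustrations.

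**Dilution.** The SME mean is 0.75 × 1.30 = 0.975, so the observed ratio is (0.975 + b)/(1.30 + b).

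**Chance of passing 60%.** Take asthma days with SD 1.5 times the mean in each arm, and unrelated days as independent Poisson with variance b:

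- SE² = [(3.8025 + b)/(1.30 + b)² + (2.1389 + b)/(0.975 + b)²]/100, where 3.8025 = 2.25 × 1.30² and 2.1389 = 2.25 × 0.975².
- Prior SD of the log ratio = ln 3/1.96 = 0.5605, variance 0.3142. Weight w = 0.3142/(0.3142 + SE²).
- Chance = Φ(−ln(ratio)/SE − 0.2533/√w).

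| b | Ratio | SE | Chance |
|---|---|---|---|
| 0 | 0.750 | 0.2121 | 0.861 |
| 0.25 | 1.225/1.55 = 0.790 | 0.1811 | 0.849 |
| 0.5 | 1.475/1.80 = 0.819 | 0.1594 | 0.838 |
| 1.0 | 1.975/2.30 = 0.859 | 0.1309 | 0.817 |

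**The plan's own figure.** The plan states power of 0.80. The b = 0 row gives 0.86, or 0.85 with a common dispersion parameter, so 0.80 is not reproduced. The difference is on the cautious side and is not part of this point.

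**Sensitivity.**

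- *Base 1.14:* the ratios are 0.795, 0.826 and 0.867, and the chances 0.85, 0.83 and 0.81.
- *Total SD kept at 1.5 times the total mean after unrelated days are added:* with base 1.30 the chances are 0.80, 0.75 and 0.67. The loss in power therefore depends on the variance assumption; the shift in the ratio does not.
- *Planning rates already include unrelated care:* the reduction is 25% times the asthma share. At an assumed share of 75% it is 18.75%.

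**Costs.** If unrelated care has the same mean cost in both arms, that mean cancels in the absolute difference and only its variance stays. A cost ratio from the planned log-link model would move toward 1 as the day ratio does. No cost mean or SD is given, so neither effect can be sized.

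**The case against.** A reader might infer that the plan counts hospital and ED care for any cause. The documents do not say so. The title frames the trial as utilization for pediatric asthma, and the asthma phrase in "ask if their child had been admitted, visited the emergency room, had a clinic appointment for asthma" can be read as covering the whole series. The follow-up script is a listed attachment whose text is not available. Study Procedures speaks of the costs of the visits collected, so costing may simply follow whichever visits are captured. This objection stands against the firm reading. It does not remove the gap: the intended cause has to be inferred, and the component wordings differ.

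A reader might also infer that unrelated stays would overwhelm the cost comparison. The planned saving in hospital days is 0.25 × 60 = 15 per 100 children, so one unrelated 15-day stay in the SME arm would offset it in days. That is one hypothetical child counted in days, not dollars. Without a cost variance it shows nothing about the cost result. All-cause cost can also be a deliberate choice under a health-system perspective, though the plan does not say that it is.

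Serious damage to power is not shown either. With independent unrelated days the loss is about 4 points even at 1.0 added day. Larger losses need both high unrelated use and the stricter variance assumption, and the exclusion of other chronic conditions makes high use less likely.

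The best argument against changing the endpoint is attribution. Families are unblinded, and SME families receive extra teaching on triggers and symptoms, so a parent-reported reason could differ by arm. This stands as a cost of the fix. However, the plan already relies on a parent-stated reason for clinic visits, and blind classification with an all-cause analysis alongside limits the exposure.

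**Conclusion.** The point holds as a gap in definition. The outcome and cost texts do not limit hospital and ED care to asthma, the monthly question limits at least the clinic item, and no attribution rule exists. Followed literally, the primary total mixes two scopes.

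The consequence is attenuation of the rate ratio, from 0.75 to between 0.79 and 0.86 over the assumed range of 0.25 to 1.0 unrelated days per child-year. The loss in the chance of success is modest if those days are independent of asthma days. These figures rest on assumed rates, on 1.30 rather than the stated 1.14 days, and on planning rates that contain no unrelated care. The true size cannot be derived from the documents, for days or for costs. The plan should be changed, chiefly because the choice governs what is collected: reasons for care outside the health system may not be recoverable later.

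**What to change.** 1. Define treatment days, and the utilization costs compared with them, as asthma-related in every component: hospital, ED and clinic. Use the same wording in Specific Aims, Outcomes (including the cost paragraph) and Study Procedures.
2. Set the attribution rule in writing: recorded primary diagnosis for MHHS and UTHealth encounters, parent-reported reason for care elsewhere. Have it applied by someone blind to arm.
3. In the monthly contact, ask and record the reason for each admission and ED visit, and align the follow-up script.
4. Report all-cause days and all-cause health-system costs as a sensitivity analysis.

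The cost is wording in those sections, one questionnaire item, and a diagnosis filter on records already being obtained. The downside is some misclassification of reason, possibly differential for parent-reported outside care because families are unblinded. The all-cause analysis is the check on that.

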All statistical and economic analyses will be conducted under the intent-to-treat analyses principle using generalized linear models with appropriate link function based on data distribution (ie, negative binomial or Poisson with log link). All Bayesian models will use neutral, vaguely informative prior such as those with relative risk centered at 1 with credible interval range from 0.3-3.0 encompassing the largest likely effect size for major outcomes in RCTs. Cost differences between the two arms will be assessed using generalized linear models with log-link and gamma distribution. To account for patients who may not be hospitalized or incur hospital-related costs during the study period, zero-inflated models will be considered. All models will be adjusted for stratifying variables (asthma control, recruitment site, and age) and account for patient clustering as necessary. Optimal model fit for each outcome will be determined from model diagnostics and comparison of likelihood-based statistics. All analyses will be conducted in R.

Data Storage and Handling: We will use Research Electronic Data Capture (REDCap) to randomize patients and collect predefined study data needed to address each of our hypotheses. REDCap is a secure, web-based application designed to support data capture for research studies, providing: 1) an intuitive interface for validated data entry; 2) audit trails for tracking data manipulation and export procedures; 3) automated export procedures for seamless data downloads to common statistical packages; and 4) procedures for importing data from external sources

Study Procedures: Participants will be approached for enrolment during their index hospitalization. Consent will be obtained. Study duration will last one year from enrolment. Participants will be contacted once a month (12 contacts total) to assess healthcare utilization within that past month. The PI on enrollment will ask for several different methods of contact and ask which the participants prefer ie. calling - what times of day/day of week, emailing, texting, directly messaging on social media etc. The PI will contact each participant by their mode of preference once a month. During the follow up contacts, participants will also be asked a short questionnaire (approximately 10 minutes).

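### Treatment days rest mainly on unblinded parents' reports to the investigator who delivers SME, with records used only as a check and no rule for disagreement, so arm-dependent reporting could enter the primary effect

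*Combined protocol and SAP*

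**What the plan says.** The primary outcome (Outcomes) is "Total number of treatment days in a medical setting (hospital, ED, clinic) within one year of enrollment". On its source, the same section says "Healthcare utilization will be primarily assessed by parental report", and describes collection as follows: "The PI will contact families every month and ask if their child had been admitted, visited the emergency room". Study Procedures repeats the arrangement: "The PI will contact each participant by their mode of preference once a month", for 12 contacts in all.

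Records come second: "We will also verify utilization of any of the 14 Memorial Hermann hospitals (MHHS) and the UT Health clinics", using electronic medical records and claims. No source other than parent report is named for care elsewhere. No rule says which source counts when report and record differ.

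The investigator who makes these contacts is also responsible for enrolment and randomization (Randomization, Consent, Allocation, Blinding) and sends out the posts (Interventions, Social Media Enhanced Education). The cost paragraph of Outcomes describes this investigator as the person "who will be primarily responsible for managing the social media intervention".

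On blinding, the plan says: "While patients and caregivers cannot be blinded, the statistician and healthcare economist will be". No blinded outcome assessor is named. The only measurement bias that the plan discusses is recall bias, which it answers with monthly contact.

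**The concern.** The outcome depends on what an unblinded parent tells an unblinded investigator, and in one arm that investigator is also the person providing the education. SME families can message the team and post questions to it throughout the year; control families have no matching channel. Outcome contact may itself take place over social media if the family prefers it. Both features could make reporting differ between arms.

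A monthly interval shortens recall, but it does not address reporting that depends on arm. A blinded statistician analyses whatever counts were recorded, so blinding at that stage cannot undo a difference that arose at collection. Any such difference multiplies the relative risk (RR) for treatment days directly.

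The plan already obtains a source that does not depend on the conversation. For costs, it draws MHHS emergency visits and hospitalizations from the cost-accounting system and UT Health clinic visits from claims. The same encounter could thus be counted from a record for one outcome and from parent report for another.

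**Working it through.** **Inputs from the plan** (Randomization section and Data Analysis Plan): 200 patients allocated 1:1, taken as 100 per arm; negative binomial counts with SD 1.5 times the mean; prior RR centred at 1 with interval 0.3 to 3.0; benchmark of more than 60% probability of benefit; assumed RR 0.75.

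**Inputs assumed:** the reporting difference between arms and the share of days that records settle. The documents give neither, so both are shown as ranges.

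**Formula.** I use a normal approximation on the log scale, as the plan's power paragraph does.

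- Standard error of log RR: SE = sqrt(2 × 1.5² / 100) = sqrt(0.045) = 0.212.
- Prior SD of log RR, reading the interval as 95%: ln(3.0/0.3) / (2 × 1.96) = 0.587. Using ln(3)/1.96 = 0.56 instead changes the results below by no more than 0.001.
- Weight on the data: w = 0.587² / (0.587² + 0.212²) = 0.885.
- The posterior probability of benefit exceeds 0.60 when −(estimated log RR)/SE > 0.2533/sqrt(w) = 0.269.
- Chance of that: Φ(−ln(apparent RR)/0.212 − 0.269).

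**The plan's own figure.** At RR 0.75: Φ(1.356 − 0.269) = 0.86, against a stated power of 0.80. Simulating 1,000 negative binomial trials per setting gave 0.86 to 0.87. The stated figure is not reproduced. Separately, the plan's components give 25 × 2.4 + 35 + 35 = 130 days per 100 children, where the plan states 114. This point depends on neither discrepancy: with SD tied to the mean as above, SE does not involve the mean.

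**No true effect, records correct nothing.** Apparent RR = SME reporting relative to control.

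| SME reporting vs control | Apparent RR | Chance of >60% |
|---|---|---|
| equal | 1.00 | 0.39 |
| 5% fewer days | 0.95 | 0.49 |
| 10% fewer | 0.90 | 0.59 |
| 20% fewer | 0.80 | 0.78 |
| 5% more | 1.05 | 0.31 |
| 10% more | 1.10 | 0.24 |

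Simulation at apparent RR 1.00, 0.95, 0.90 and 0.80 gave 0.42, 0.50, 0.59 and 0.81.

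**No true effect, records settle a share s of days.** Only the remaining 1 − s rests on report, so apparent RR = 1 − u(1 − s) for under-reporting u.

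| u | s (assumed) | Apparent RR | Chance of >60% |
|---|---|---|---|
| 10% | 0.70 | 1 − 0.10 × 0.30 = 0.97 | 0.45 |
| 20% | 0.70 | 1 − 0.20 × 0.30 = 0.94 | 0.51 |
| 10% | 0.90 | 1 − 0.10 × 0.10 = 0.99 | 0.41 |
| 20% | 0.40 | 1 − 0.20 × 0.60 = 0.88 | 0.63 |

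**With a true RR of 0.75**, 10% under-reporting gives an apparent RR of 0.675 and moves the chance from 0.86 to 0.94. The probability of benefit then hardly separates the two cases, but the reported size of benefit is exaggerated.

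**The case against.** The strongest reply is that the plan may already do what is asked. To verify ordinarily means to check and correct. If in-network records override parent report, the plan as written already sits at 0.45 or 0.51 (with the assumed 70% share), and a rule in writing changes nothing numerically. This stands: a reader might infer that parent report prevails over the record, but the text does not say so. What can be shown is the missing rule.

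A reader might also infer that SME families will report fewer visits to please the investigator. The documents do not support a direction. Closer contact could equally bring out more visits, and that would hide a real benefit. Nor is familiarity confined to SME: the same investigator has primary responsibility for enrolling both arms and makes the monthly contacts in both.

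The 0.39 under no effect comes from the 60% benchmark, not from the data source. That benchmark appears in the power statement, and the plan says it avoids arbitrary thresholds for defining success. The figures therefore illustrate sensitivity; they are not error rates of a declared decision rule.

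The plan also lists a follow-up script (content not shown) and a short questionnaire. These may standardize the questions, but they do not blind the person asking or the person answering. Finally, families cannot be blinded and this is a pilot. Both are true, but its conclusions are meant to rest on the observed effect and to guide expansion, and the record data are already being obtained.

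**Conclusion.** The point holds as an open route to bias, not as a demonstrated bias. The overlap of roles, the primacy of parent report, the checking role given to records and the lack of a rule for disagreement are all in the text. The direction and size of any differential reporting are unknown, as is the share of care delivered in MHHS and UT Health.

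On the stated assumptions, settling 70% of days from records lowers the chance of a falsely favourable result by 0.59 − 0.45 = 0.14 at 10% under-reporting and by 0.78 − 0.51 = 0.27 at 20%. The gain is zero if the plan already intends records to override. The values 0.59 and 0.78 should not be read as properties of the plan as written, because they suppose that verification corrects nothing.

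This is a worthwhile, inexpensive improvement that should be made. It does not show the design to be unsound.

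**What to change.** In Outcomes:

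1. State that treatment days at MHHS hospitals and UT Health clinics are counted from the medical record and claims in both arms, extracted without reference to arm, and that the record overrides parent report.
2. Use parent report only to add encounters outside those systems.
3. Pre-specify a records-only sensitivity analysis of the primary outcome.
4. Keep the monthly contact by each family's preferred mode, with the same script in both arms. Replacing it with a survey is not advised: it could raise non-response, possibly unequally by arm.

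The cost is mainly protocol wording and arm-blind extraction from sources the plan already uses; no new data source is needed. Two limits remain. Outside encounters still rest on unblinded parent report, and the records-only analysis misses them. The two analyses should therefore be read together.

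### Outside-MHHS hospital stays are costed from a mean per encounter with no stated scaling for length of stay; a pooled mean would mildly dilute any stay-length difference in the cost comparison

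*Combined protocol and SAP*

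**What the plan says.** The cost paragraph under Outcomes sets two rules for hospital care. Inside the system: "For each ED visit and hospitalization in the MHHS, total hospital-specific costs will be obtained from the cost-accounting system for these hospitals". Outside it: "The costs at other hospitals outside MHHS will be estimated based on the mean costs of these encounters at MHHS". The unit named in the second rule is the encounter. The text does not say whether the mean is pooled over arms or whether it depends on length of stay.

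The Primary Outcome paragraph works in days: "Treatment days are defined as the summation of days in the hospital, ED, or in the clinic". The costs are secondary outcomes, listed as "total estimated health system costs, hospital costs, and clinic costs". Reduced total health system cost is the third hypothesis.

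On data collection, the monthly contact will "ask if their child had been admitted, visited the emergency room, had a clinic appointment for asthma, or missed any days of school", and the protocol's closing data list reads: "Information to be gathered will be missed school days, total number of hospitalizations, emergency room visits, and clinic visits". Neither names length of stay. Checking against records is described only within the system: "We will also verify utilization of any of the 14 Memorial Hermann hospitals (MHHS) and the UT Health clinics". The sample-size section fixes stay length for planning: "Each admission accounts for 2.4 treatment days, and each clinic and ER visit accounts for 1 treatment day".

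**The concern.** An outside stay is measured in two ways. In the primary outcome it counts by its days. In the cost outcome, on the plain reading, it is one average MHHS encounter, whereas an MHHS stay carries its own cost. On the planning figure of 2.4 days, and if cost were proportional to days, an 8-day outside stay would be priced at 2.4/8 = 30% of its value and a 1-day stay at 2.4/1 = 240%.

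Errors of that kind largely average out within an arm. What does not average out is a difference between arms in mean stay length: a mean pooled over arms gives both arms the same price per outside stay. The cost comparison would then show less of such a difference than the day count does, and the two results could diverge because of the costing rule alone. Cost reduction is one of the two benefits for which the plan wants a Bayesian probability, so the rule deserves to be exact.

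**Working it through.** The plan gives no figure for the effect of its costing rule, so there is none to reproduce. The check asks what the stated rule would return under explicit assumptions.

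**Inputs from the plan.** 100 patients per arm (200 randomised 1:1); 25% readmission rate under usual education; 2.4 days per admission; 25% expected effect, so a ratio of 0.75.

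**Assumptions, not in the plan.** Outside share *p* of 20%, 30% or 50%, equal in both arms; stays alike inside and outside; one MHHS mean pooled over arms. Let *rn* be the SME/usual ratio of number of stays and *rl* the ratio of mean cost per stay (equal to the length ratio if cost is proportional to days).

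**Formula.** With the usual-care mean cost per stay set to 1, the pooled MHHS mean is m = (rn·rl + 1)/(rn + 1). The rule returns

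ratio = rn·[(1−p)·rl + p·m] / [(1−p) + p·m].

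**Half fewer, half shorter stays** (rn = rl = 0.866, true ratio 0.75). m = 1.75/1.866 = 0.938.

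| p | Calculation | Ratio returned | Log effect lost |
|---|---|---|---|
| 20% | 0.866 × 0.880/0.988 | 0.772 | 10% |
| 30% | 0.866 × 0.888/0.981 | 0.783 | 15% |
| 50% | 0.866 × 0.902/0.969 | 0.806 | 25% |

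**Mostly fewer stays** (0.80 × 0.94 = 0.752). m = 1.752/1.8 = 0.973. The rule returns 0.761 at 20% and 0.776 at 50%, a loss of about 4% and 11% of the log effect.

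**Only fewer stays** (rl = 1). Then m = 1 and the ratio is rn at every *p*: no bias.

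**Only shorter stays** (rn = 1). The cost difference kept is (1−p): 80%, 70% and 50% at shares of 20%, 30% and 50%. Arm-specific means would keep 100% if the effect were equal inside and outside.

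**Against the trial's precision.** Take 25 admissions under usual care and 25 × 0.866 = 21.7 under SME, Poisson counts, and a coefficient of variation of 0.8 for stay length (assumed), with cost proportional to days. The standard error of the log cost ratio is √(1.64/25 + 1.64/21.7) = 0.38, where 1.64 = 1 + 0.8². The shifts from 0.75 on the log scale are 0.029, 0.043 and 0.072, or about 0.08, 0.12 and 0.19 standard errors. At a 20% share the rule touches about 0.2 × 46.7 = 9 admissions.

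**Choice of remedy.** If cost per stay is a + b·days, a regression with an intercept recovers both parts and keeps the whole difference. A pooled mean cost per day does so only if a = 0. If half the cost is fixed per admission, it turns a stay-length-only difference into about 111% of its true size at a 10% share and 153–157% at 50%.

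**The case against.** The strongest objection is that this bias needs an effect the plan never proposes. The effect size rests on cited reductions in admissions, emergency visits and clinic visits; planning holds stay length at 2.4 days; no hypothesis concerns length of stay. That stands: effects on the number of stays pass through the costing rule untouched, and the half-and-half split above is only an illustration. The direction is open too. If SME mainly prevented short admissions, the remaining stays would be longer on average, and the rule would flatter SME.

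A reader might infer that every outside admission is priced at one flat mean and that any SME effect on stay length is erased. The documents do not go that far. They say costs will be estimated on the basis of MHHS means and leave pooling and stratification open. Pooling is the more natural reading, since the health economist is to be blinded and each arm would have only about 25 admissions, but it remains an inference. Even under pooling, the effect is lost only from the outside stays.

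A reader might also infer that replacing real costs by a mean narrows the intervals misleadingly. Simulation under the same assumptions (4,000 trials per setting) gave coverage for the arm difference of 0.94–0.95 at outside shares of 20–30% and 0.93–0.95 at 50%, so this is not a practical problem.

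Finally, the remedy needs the length of outside stays, which the described monthly questions and data list do not name. The follow-up script is not available to read, so it may ask. But the primary outcome cannot be computed for those stays without it, so the remedy adds no new requirement.

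**Conclusion.** A minor point that holds as a cheap improvement. The rule as written prices outside stays per encounter without scaling for length, beside actual costs for MHHS stays and a primary outcome in days. If the mean is pooled, a stay-length difference between arms is diluted in hospital costs roughly in proportion to the outside share. The illustrated size is 0.77 to 0.81 in place of 0.75 for shares of 20% to 50%, and nothing at all if only the number of stays changes. The figures rest on an outside share the plan does not state, an assumed split of the effect, and equal shares and similar stays inside and outside. They cover admission costs only, whereas total cost also includes ED visits, clinic visits and SME personnel time. The shift is small against sampling error on a secondary outcome of a pilot, and it does not touch the primary outcome.

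**What to change.** Replace the sentence on costs at other hospitals with:

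> Hospital stays outside MHHS will be priced from a regression of cost on length of stay (with intercept) fitted to MHHS asthma stays, pooled over arms, using the stay length recorded for the primary outcome. Outside ED visits will be priced at the MHHS mean ED cost. The per-encounter mean will be used only where stay length is unknown, and the number of such stays will be reported by arm.

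Do not use a simple mean cost per day, which overstates a stay-length difference when part of the cost is fixed per admission. State in Study Procedures that the monthly contact records the length of each outside stay.

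The cost is a short text change, one question at follow-up that the primary outcome already needs, and a simple regression on MHHS cost data the plan already obtains. The downside is that outside costs then carry any error in parent-reported stay length.
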